8.5.5 RELATIONSHIP TO STUDY INTERVENTION

All AEs will have their relationship to the study device and the index procedure assessed by the investigator and the Sponsor. All aspects of past medical history, current comorbidities, other reported adverse events, and protocol defined criteria will be reviewed to provide a determination of device or procedure relationships. The Clinical Events Committee (CEC) will review events as prescribed in the Study CEC Charter. The following definitions will be used to guide investigator, sponsor and CEC assessments:

- **Device Related** – Complication associated with the device design as it relates to placement, efficacy or durability, which may involve the delivery system
- **Procedure Related** – Complication associated with the initial placement of the device or any necessary secondary intervention. This includes morbidity associated with either anesthesia or surgical procedure. This also includes inappropriate patient selection and errors attributed to inappropriate operator techniques, measurements or judgment

The degree of certainty about causality will be graded using the categories below:

- **Definitely Related** – There is clear evidence to suggest a causal relationship, and other possible contributing factors can be ruled out. The clinical event, including an abnormal laboratory test result, occurs in a plausible time relationship to study intervention administration.

- **Probably Related** – There is evidence to suggest a causal relationship, and the influence of other factors is unlikely. The clinical event, including an abnormal laboratory test result, occurs within a reasonable time after administration of the study intervention.
- **Possibly Related** – There is some evidence to suggest a causal relationship. However, other factors may have contributed to the event (e.g., the participant's clinical condition, other concomitant events). Although an AE may rate only as "possibly related" soon after discovery, it can be flagged as requiring more information and later be upgraded to "probably related" or "definitely related", as appropriate.
- **Unlikely to be related** – A clinical event, including an abnormal laboratory test result, whose temporal relationship to study intervention administration makes a causal relationship improbable and in which other drugs or chemicals or underlying disease provides plausible explanations (e.g., the participant's clinical condition, other concomitant treatments).
- **Unrelated** – The AE is completely independent of study intervention administration, and/or evidence exists that the event is definitely related to another etiology. There must be an alternative, definitive etiology documented by the clinician.

In any instance of uncertainty, the more conservative assessment will be used.

8.5.6 EXPECTEDNESS

Expected adverse events that could potentially occur during the course of the investigation and follow-up are called anticipated adverse events. These events must be reported if clinically significant. Anticipated AEs are listed below:

- Access site complications and sequelae (e.g., dehiscence, infection, pain, hematoma, pseudoaneurysm)
- Allergic reaction to contrast agent (e.g., pruritus, urticaria, bronchospasm, angioedema, hypotension or anaphylaxis that occurs during or post-procedure)
- Amputation
- Anesthetic complications and sequelae (e.g., aspiration)
- Aneurysm enlargement
- Aneurysm rupture
- Arterial damage or trauma (e.g., bleeding, perforation, dissection, rupture)
- Arterial or venous thrombosis and/or pseudoaneurysm
- Arteriovenous fistula
- Bleeding requiring transfusion and/or surgical intervention
- Bowel complications (e.g., ileus, ischemia, infarction, necrosis)
- Cardiac complications and sequelae (e.g., arrhythmia, myocardial infarction, congestive heart failure, hypotension, hypertension)
- Catheter or implant component fragmentation and sequelae (e.g., embolization, vessel trauma)
- Claudication
- Coagulopathy
- Death (due to any cause)
- Edema
- Embolization (micro and macro) with transient or permanent ischemia or infarction
- Endoleak (Type Ia, Type Ib, Type Ic, Type II, Type IIIa, Type IIIb, Type IV)
- Fever and localized inflammation

- Genitourinary complications and sequelae (e.g., ischemia, fistula, incontinence, hematuria, impotence, infection)
- Gutter leaks
- Hepatic failure
- Infection of the aneurysm, device(s), device access site, including abscess formation, transient fever and pain.
- Local or systemic neurologic complications and sequelae, transient or permanent (e.g., stroke, transient ischemic attack, paraplegia, paraparesis, paralysis, numbness and/or tingling in legs)
- Lymphatic complications and sequelae (e.g., lymph fistula)
- ChEVAS System: improper component placement; incomplete component deployment; component migration; component stenosis/compression; occlusion/thrombosis; infection; stent fracture; EndoBag damage or separation; dilatation; erosion; loss of integrity; polymer leak, puncture and perigraft flow
- Thrombosis or occlusion of stent graft or arterial vessel of the lower extremities
- Pulmonary/respiratory complications and sequelae (e.g., pneumonia, respiratory failure, prolonged intubation, pulmonary embolism)
- Post-implant syndrome
- Renal complications and sequelae (e.g., artery occlusion, infarction, insufficiency, failure)
- Secondary Intervention
- Surgical conversion to open repair

Updates to the IFU, Investigator Brochure, or updated reporting guidelines may affect the anticipated adverse events.

8.5.7 TIME PERIOD AND FREQUENCY FOR EVENT ASSESSMENT AND FOLLOW-UP

Adverse events will be assessed at each follow-up visit at a minimum. Should the investigator become aware of an adverse event outside of protocol-defined intervals, these will be reported to the Sponsor within the applicable time frame.

8.5.8 ADVERSE EVENT REPORTING

For all adverse events occurring during the study period, data must be entered in the Adverse Event eCRF in the EDC system. For serious adverse events (SAEs), the section of the eCRF describing the serious nature of the AE must also be completed. The PI should supply to Endologix and the responsible EC/IRB any redacted source documentation and information (e.g., other diagnostic testing, discharge reports, autopsy reports, etc.) as it is available. All adverse events reported in the database or discovered in source documentation will be investigated by Endologix.

8.5.9 SERIOUS ADVERSE EVENT REPORTING

Serious Adverse Events (SAE) with a procedure or device relationship will be reported to the Sponsor within 2 working days of site awareness. SAEs with no device or procedure relationship will be reported to the Sponsor within 5 business days of site awareness.

Death – for any death, regardless of cause or timing, it is recommended that the site notify the Endologix Clinical Department via the EDC system within 1 working day of awareness. The PI should supply to Endologix and the responsible EC/IRB with any redacted source documentation and information (e.g.,

death summary, autopsy report). In all cases, every attempt should be made to obtain as much detailed information on the events or conditions leading up to the death as possible.

8.5.10 MAJOR ADVERSE EVENTS

Major Adverse Events (MAE) are defined as below and will be adjudicated by the Clinical Events Committee.

Major Adverse Event: An event occurring during the study that meets one of the following criteria:

- *All-Cause Death*: Any death occurring during the study period, regardless of cause. Death will be further categorized as one of the following:
 - *Aneurysm-related death* – any death occurring within 30 days from the date of the procedure, regardless of cause, and death due to aneurysm rupture or following any procedure intended to treat the aneurysm
 - *Cardiac-related death* – death due to arrhythmia, heart failure (including cardiogenic shock), or myocardial infarction
 - *Pulmonary-related death* – death due to pulmonary edema, respiratory failure, or pulmonary embolism
 - *Vascular-related death* – death due to stroke, cerebral hemorrhage, or other clear vascular event that is not categorized as cardiac-related, pulmonary-related or aneurysm-related
 - *Other* – a death that cannot be clearly categorized as above, but where information on the circumstances of death is available
 - *Unknown* – a death where no information is available
- *Bowel Ischemia*: The lack of adequate blood flow to the intestines that requires intensification of medical therapy or surgical/endovascular intervention
- *Paraplegia*: Paralysis of the lower extremities inclusive of the lower trunk, with deficits present at the subsequent scheduled follow-up visit
- *Renal Failure*: renal injury resulting in the need for temporary or permanent dialysis
- *Disabling Stroke*: new neurological deficit resulting from vascular insult confirmed by imaging. Disabling is considered a value of 2 (slight disability) or above on the modified Rankin Scale (mRS)

8.5.11 ADDITIONAL ADVERSE EVENT DEFINITIONS

Additional events or occurrences of interest that have relevance to the study device, therapy, disease, re-intervention or evaluations to be captured for endpoint analysis are as follows:

- *Abdominal Aortic Aneurysm Rupture* – intra-operative or post-procedural rupture through the aneurysm wall within the stented segment of the aorta
- *All-Cause Mortality* – Death from any cause
- *Aneurysm Related Mortality* – death reported within 30 days of the index endovascular procedure, due to aneurysm rupture, within 30 days of re-intervention or conversion to open repair, or as otherwise determined by the Clinical Events Committee
- *Aneurysm Sac Enlargement* – aneurysm sac diameter increase of >5mm in late follow-up as compared to the initial post-operative measurement (30 day follow-up)
- *Conversion to Open Repair* – open surgical repair of the abdominal aortic aneurysm due to unsuccessful delivery or deployment of the stent graft and/or renal stents, due to complications or other clinical situations that precluded successful endovascular treatment, or at any time

following initial successful endovascular treatment for any reason. Conversion to Open Repair shall always be captured as a re-intervention

- *Distal Ischemia* – New onset of compromised peripheral blood flow resulting in femoral or peripheral arteria occlusion or stenosis (attributable to the index procedure and not related to natural progression of atherosclerotic disease) causing a threat to the viability of the limb and requiring surgical or percutaneous intervention
- *Endoleak* – Clear evidence of contrast outside of one or both EndoBags, which communicates with the aneurysm sac
 - *Type Ia* – originating proximally at the infrarenal segment
 - *Type Ib* – originating distally
 - *Type Ic* – originating at a chimney stent (visceral vessel)
 - *Type II* – originating from a patent lumbar artery, inferior mesenteric artery, or other collateral visceral vessel
 - *Type III* – between components, if an extender is used
 - *Type IV* – trans-device
- *Gutters* – Clear evidence of contrast outside of one or both EndoBags, which does not communicate with the aneurysm sac
- *Implant Occlusion* – Radiological finding indicating 100% blockage of device lumen
- *Luminal Thrombus* – endograft thrombosis resulting in any endovascular or surgical intervention after completion of the Nellix system implantation
- *Migration* – CoreLab reported individual stent distal movement >5mm from the original implant location relative to the center of the distal renal artery
 - *Clinically Significant Migration* – CoreLab reported distal movement >10mm from the original implant location relative to the center of the distal renal artery resulting in an intervention or serious complication
- *Secondary Procedure* – any non-diagnostic surgical intervention after the index procedure intended to correct or repair any site reported endoleak, gutters, device occlusion, migration, aneurysm sac expansion and/or a device defect, including infection
- *Stent Thrombosis* – Blood clot that results in stenosis or occlusion of a stent
- *Thromboembolic Event* – Blood clot that has broken loose and is carried distally

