³ Defined as, at the conclusion of the procedure, a > 10mm difference between the top of the Nellix stents, or the top of a visceral stent being > 14mm below the Nellix stent (the bag shelf is 4mm below the top of the Nellix stents).

⁴ Concomitant procedures, including those for infrequently encountered circumstances, may be anticipated and prepared for as part of a comprehensive endovascular approach

of adjunctive stents that are part of the defined system, does not result in technical failure.⁵

- c. Successful withdrawal (i.e., successful withdrawal of the delivery systems without the need for unanticipated corrective intervention related to withdrawal).

Multiple events occurring to a subject are considered a single subject failure for the purposes of calculating the composite one-month rate, as the rate is based on the total number of subjects. Since none of these variables are restricted by imaging requirements for detection, the cutoff date for the endpoint is exactly 30 days from the index procedure.

3.2 1-YEAR PRIMARY ENDPOINT

The primary 1-year endpoint is a blend of safety and effectiveness indicators. The endpoint is defined as the absence of:

- Abdominal aortic aneurysm rupture (0 - 365 days);
- Aneurysm-related mortality (0 – 365 days)
- Imaging-determined events at the 12-month imaging window. These do not require an intervention within 12 months to count as events:
 - Type I or Type III endoleak
 - Migration⁶ > 10mm
 - Sac Expansion⁷ > 5mm
 - Loss of Patency (100% occlusion) in Branches⁸, Nellix, or iliac limbs not seen at the index procedure
- Open conversion through day 365

⁵ Examples of acceptable procedures include:

- Placing an additional stent (Verta or Lifestent) to correct kink in visceral vessel (or a kink in the stent resulting from the vessel anatomy) or to smooth transition from Verta to visceral vessel (transition stenting)
- Placing an additional stent (Verta or Lifestent) to treat pre-existing visceral artery stenosis (spot stenting)
- Placing Verta stent within initial Verta stent due to length discrepancy, need to achieve a Verta length not covered by available lengths, or inadequate initial seal
- Placing Ovation limb to extend Nellix in order to obtain an adequate distal seal;
- Coiling of non-treated branch vessels
- Ballooning of any vessel or stent

⁶ As measured by the proximal end of the Nellix stents relative to the reference artery

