⁷ As measured across the maximum transverse sac diameter relative to the 1-month scan

⁸ Branches refer to stents in the left renal artery, right renal artery, and superior mesenteric artery

- Other major device-related⁹ surgical or endovascular re-interventions through day 365 for:
 - Type I or III endoleak, or gutters
 - Migration
 - Thrombotic events/Occlusions - complete loss of patency in any of the components of the ChEVAS System due to thrombotic events and/or device deformation
 - Device deformation resulting from fracture, that leads to clinical sequelae of vessel stenosis progressing to decreased perfusion, or puncturing of graft material leading to endoleak
 - Relining of the Nellix Stents to correct stenosis or kink
 - Mal-deployed device that leads to clinical sequelae of migration, endoleak, or thrombosis
 - Device infection

Non-major interventions are not included in the endpoint:

- Endovascular intervention for branch stenosis (within the stent or distal to the stent) for a reason other than stent fracture
- Interventions for Type II endoleaks
- Non endovascular treatments for procedural complications that are non-device specific, e.g., seroma, surgical site infection etc.

The 1-year endpoint is a collection of variables that may be detected at any time or require imaging to be detected. As such, variables are evaluated differently for the “1-year” timeframe. Variables lacking imaging restrictions (rupture, mortality, interventions) are evaluated until day 365 for the 1-year endpoint as the exact day of the event will be known. Onset dates for imaging-driven variables are unknown (they have may occurred at any time prior to the imaging scan that detected them) and thus are evaluated at the one-year imaging window as determined by the scan date. Presence of positive imaging-related findings within the 1-month or 6-month imaging windows does not factor into the endpoint analysis. Rather, the endpoint analysis restricts positive findings to only those within the 1-year imaging window. Imaging results used in the endpoint analysis will be sourced from core lab assessments.

In contrast to classic EVAR studies that analyze safety at 1 month and effectiveness at 1 year, the ChEVAS study is designed to evaluate both safety and effectiveness across dual endpoints (thus, passing both endpoints will indicate the trial has demonstrated safety and effectiveness).

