3.3.4 OUTCOMES

Additional outcomes will be collected for each follow-up time point through 5 years post procedure. All outcomes will be differentiated, where appropriate, by the stents involved (Nellix vs. Verta stents)

- Mortality (all-cause and aneurysm-related)
- MAE Individual Components
- Aneurysm Rupture
- Conversion to Open Repair
- Adverse Events
- Renal Function (assessed via creatinine and eGFR)
- All Types of Endoleak (Ia, Ib, Ic, II, III, IV, or unknown)

- Gutters
- Device Patency and Integrity
 - Stenosis
 - Occlusion
 - Kinking
 - Fracture
- Aneurysm Sac Diameter
- Migration (e.g., migration > 5 mm, migration > 10 mm, clinically significant migration)
- Secondary Procedures
 - All Types of Endoleaks
 - Device stenosis/occlusion
 - Device kink
 - Device fracture
 - Luminal thrombus
 - Rupture
 - Migration
 - Aneurysm sac expansion
 - Device defect
 - Gutters

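### The Type III and Type IV endoleak definitions in Section 8.5.11 conflict with Section 8.5.6 and, read literally, leave some device-integrity leaks out of the 1-year primary endpoint

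*Combined protocol and SAP*

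**What the plan says.** Section 3.2 lists the imaging events for the 1-year endpoint. For endoleak the entry is "Type I or Type III endoleak", and of the imaging events generally it says "These do not require an intervention within 12 months to count as events". Imaging results come from the core lab, and only findings in the 1-year window count.

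Section 3.2 also counts certain major re-interventions through day 365. Those bearing on leaks are for Type I or III endoleak or gutters, for fracture-related device deformation including "puncturing of graft material leading to endoleak", and for a mal-deployed device with endoleak among its consequences. Interventions for Type II leaks are expressly left out. Interventions for Type IV leaks or leaks of unknown type are on neither list.

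Section 8.5.11 introduces its definitions as serving the endpoint analysis. An endoleak is "Clear evidence of contrast outside of one or both EndoBags, which communicates with the aneurysm sac". Type Ic arises at a chimney stent, Type III is a leak "between components, if an extender is used", and Type IV is a leak across the device, with no restriction to intact material.

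Section 8.5.6 lists as anticipated events "Endoleak (Type Ia, Type Ib, Type Ic, Type II, Type IIIa, Type IIIb, Type IV" and, in a separate entry for the ChEVAS System, "EndoBag damage or separation; dilatation; erosion; loss of integrity; polymer leak, puncture and perigraft flow". Section 3.3.4 collects "All Types of Endoleak (Ia, Ib, Ic, II, III, IV, or unknown" as an additional outcome.

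**The concern.** A leak through torn or punctured device material is a failure of the device. Section 3.2 accepts this in part, since it treats fracture-related puncture with endoleak as a major event, but only once there is a re-intervention. Other imaging events need no intervention to count. Under Section 8.5.11 the only label that fits such a leak is Type IV, which the imaging component omits.

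The extender condition narrows Type III further. Ovation limbs and extensions are used only when needed, and footnote 5 to Section 3.1 accepts one Verta stent placed inside another. That creates a junction between components with no extender involved.

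Each subject whose only failure is such a leak would be scored a success, so any error runs in the device's favour. The split into IIIa and IIIb in Section 8.5.6 suggests that a wider Type III was intended, but the protocol does not say so.

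**Working it through.** **Step 1: route each kind of leak through the text of Sections 3.2 and 8.5.11.**

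| Situation | Route | 1-year failure? |
|---|---|---|
| Any leak with sac expansion above 5 mm at 1 year, rupture, aneurysm-related death or open conversion | Own component of 3.2 | Yes, whatever the type |
| Graft puncture from stent fracture, with endoleak, re-intervened by day 365 | Fracture item | Yes, whatever the type |
| Mal-deployed device with endoleak, re-intervened by day 365 | Mal-deployment item | Yes, whatever the type |
| Leak at a chimney stent read as Type Ic, on the 1-year scan | Type I | Yes |
| Leak through a graft or EndoBag defect, on the 1-year scan, no other event | Type IV under 8.5.11 | No, read literally |
| Leak at a junction without an extender, not read as Ic, on the 1-year scan, no other event | Outside Type III under 8.5.11 | No, read literally |
| Re-intervention for either of the last two kinds of leak, due to neither fracture nor mal-deployment | On neither list in 3.2 | No, read literally |
| Leak of unknown type on the 1-year scan, no other event | No rule given | Unstated; neither I nor III |

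In the re-intervention row, a leak repaired before the 1-year scan may leave no imaging finding either, because 1-month and 6-month findings do not enter the analysis.

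**Step 2: reproduce the plan's own figures (Sections 9.1 and 9.2).** Inputs: goal 75%, expected success 85.7%, alpha 0.05, power at least 80%, 14% drop-out. The method is an exact one-sided binomial test, taking the smallest r with P(X ≥ r | n, 0.75) ≤ 0.05.

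- n = 103: r = 85, P(X ≥ 85 | 103, 0.75) = 0.0456, and power P(X ≥ 85 | 103, 0.857) = 85.5%.
- n = 102: power 79.8%. This is the last n below 80% (checked up to 249), so 103 is the smallest n from which power stays at or above 80%.
- 103 / (1 − 0.14) = 119.8, rounded up to 120.
- 1-month endpoint, n = 120, expected event rate 14.5%: power 85.56%, against 85.6% stated.

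The stated sample size and power therefore stand.

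**Step 3: illustrate sensitivity.** The documents give no frequency for the affected leaks, so the share s below is an assumption: the proportion of subjects with such a leak as their only failure. Two separate questions are shown, each with the pass mark of 85 of 103.

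| Assumed s | Chance of passing if true success, counting these leaks, is 75% but they are left out: P(X ≥ 85 \| 103, 0.75 + s) | Power if they are counted and the 85.7% forecast ignored them: P(X ≥ 85 \| 103, 0.857 − s) |
|---|---|---|
| 0 | 4.6% | 85.5% |
| 1% | 7.2% | 77.8% |
| 2% | 11.0% | 68.4% |
| 3% | 16.1% | 58.1% |

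One per cent of 103 is about one subject.

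**The case against.** A reader might infer that every leak through a torn graft or EndoBag escapes the endpoint. The documents do not support that. Five kinds of event count regardless of leak label: sac growth above 5 mm, rupture, aneurysm-related death, open conversion, and re-intervention for fracture-related puncture or for a mal-deployed device with endoleak. Some Verta leaks would be Type Ic and so count. An EndoBag tear is not in itself an endoleak either: the bags hold cured polymer, and the definition requires contrast outside the bag that communicates with the sac. All of this stands, and it reduces the gap to the rows marked as not counted.

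The Type IV label is also an inference. Section 3.2 counts Type III without qualification, so a leak that the core lab reads as IIIb would count. Section 9.4.2 refers to the SAP for endpoint detail, but neither that detail nor the core lab's reading rules are in the text available here, and either could settle the matter. The protocol would still contradict itself between Sections 8.5.6 and 8.5.11, in a section written for endpoint analysis.

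A reader might further infer that leaks of unknown type are scored as absent and should be failures by default. No scoring rule is stated, and default failure could turn Type II leaks into primary failures although the endpoint deliberately omits them. It is not recommended as the primary rule.

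Finally, the pass probabilities might be taken as the trial's real error rate. They are not, because the shares are assumed. The background review reports no Type III leaks in the ChEVAS series, and its results table has no Type IV row.

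**Conclusion.** The point holds as an inconsistency in definitions that narrows the 1-year endpoint. Under the wording of Section 8.5.11, two cases are not failures:

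- a core-lab leak through a graft or EndoBag defect, or at a junction without an extender and not read as Type Ic, with no other qualifying event;
- a re-intervention for such a leak that is due to neither stent fracture nor mal-deployment.

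The number of affected subjects is unknown from the documents and is expected to be small. The illustration shows only that a shift of one or two subjects in 103 is not negligible near the pass mark. The conclusion assumes that the SAP and the core lab's rules do not already define Type III more widely. Because the correction is cheap and should be made before data are seen, it is worth making.

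**What to change.** Reconcile Sections 3.2, 8.5.6 and 8.5.11, and carry the result into the SAP and the core lab's reading rules:

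- Type IIIa: a leak between any ChEVAS components, with or without an extender.
- Type IIIb: a leak through a defect, tear or puncture of device material.
- Type IV: a leak across the device without a defect.
- In Section 3.2, state that the imaging and re-intervention components count both IIIa and IIIb. A leak where two Verta stents overlap then counts whether it is read as Ic or IIIa.
- For leaks of unknown type, keep the primary rule of counting Types I and III, and add a sensitivity analysis that scores them as failures.

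These are proposed definitions, since the documents define neither IIIa nor IIIb. The cost is wording and one extra analysis, with no added visits, scans or subjects. The observed success rate may be slightly lower. If the 85.7% forecast did not allow for these leaks, power falls too, to 77.8% at an assumed 1% share, so the sponsor should confirm what the forecast included.
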